In the PROPHET trial, we intend to assess the degree of biopsy-related bleeding, measures taken to control bleeding, and potential effects of bleeding on completion of the intended procedure in 100 bronchoscopy procedures performed on single and double lung transplant recipients, randomized to prophylactic topical epinephrine versus placebo (normal saline). The study participant, physician performing the TBLB, and independent observer reviewing the procedure recording will all be blinded to the randomization. Further use of measures to control bleeding that occurs during the procedure as well as the decision to complete the procedure as planned or to abort it prematurely will be left to the discretion of the performer. In this way, we aim to elucidate a potential role of topical epinephrine in the prevention of TBLB-related airway bleeding in lung transplant recipients and assess whether the dose and volume of instillation used in our institution comprises an effective means to prevent hemorrhagic complications of TBLB.

HYPOTHESIS

We hypothesize that prophylactic instillation of topical epinephrine prior to performance of TBLB will decrease the frequency and extent of biopsy-related hemorrhage as well as result in fewer procedures being aborted earlier than intended due to bleeding complications as well as shorter overall procedure time due to the preventive effect on bleeding. Concomitantly, we hypothesize that the instillation of topical epinephrine will not be associated with a serious adverse event profile in comparison to placebo.

SPECIFIC AIMS

In this randomized-controlled double blind placebo controlled clinical trial post-lung transplant patients scheduled to receive bronchoscopy with TBLB as part of their routine standard of care will be randomized to receive a fixed dose and volume of topical endobronchial epinephrine versus matching volume of placebo which will be instilled into the target biopsy airway prior to performance of TBLB. Our study will specifically aim at providing the following information:

Aim 1: Demonstrate the feasibility of assessments of bleeding related to TBLB, including:

1. The degree of TBLB-related bleeding using a standardized grading scale used by the physician performing the procedure to quantify the degree of procedure-related bleeding.

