2. The degree of TBLB-related bleeding using a standardized grading scale used by two independent observers blinded to patient data and study drug assignment who will review a video recording of the procedure to quantify the degree of procedure-related bleeding.
3. The magnitude of inter-observer variability in grading TBLB-related hemorrhage based on review of video recording of the procedure.

Aim 2: Evaluate the hypothesis that prophylactic administration of topical epinephrine results in reductions in TBLB-related hemorrhage in lung transplant recipients, including:

1. The frequency of active measures taken to control pulmonary hemorrhage once it occurred.
2. The proportion of procedures completed as planned in terms of obtaining a predefined target number of biopsy specimens.
3. Comparison between single- and double-lung transplant recipients in terms of prevalence and degree of TBLB-related hemorrhage.
4. Identification of clinical factors associated with an increased or decreased risk of procedure-related hemorrhage.

Aim 3: Evaluate the hypothesis that prophylactic administration of topical epinephrine affects the overall efficiency of bronchoscopy with TBLB performance, including:

1. Overall duration of the bronchoscopic procedure.

2. The proportion of procedures completed as planned in terms of number of adequate biopsies obtained as assessed by the physician performing the bronchoscopy.
3. The proportion of procedures resulting in acquisition of adequate biopsy samples that allows proper pathologic evaluation of assignment of a pathologic diagnosis.

Aim 4: Explore the hypothesis that instillation of our prespecified dose and volume of topical epinephrine into the target biopsy airway is not associated with an adverse event profile that is significantly different from placebo, including:

1. The prevalence of clinically significant hemodynamic changes.
2. The prevalence of cardiac adverse events, including conduction abnormalities, arrhythmia, and myocardial ischemia.
3. The prevalence of other vascular adverse events, including stroke, mesenteric ischemia, and critical limb ischemia.
4. Identification of clinical factors associated with an increased or decreased risk of drug-related adverse events.

STUDY PROTOCOL

Overview

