 - 9.8. Date and time of scope insertion and completion of the procedure as defined by the performing bronchoscopist.
 - 9.9. Biopsy forceps brand, including outer diameter, open forceps diameter, and type of forceps (round cup, oval cup, alligator, impaling needle).
 - 9.10. Fluoroscopy time.
 - 9.11. Number of forceps passes.
 - 9.12. Total number of acquired biopsy specimens; Specimen distribution across laboratories (anatomic pathology, microbiology, other laboratory).
 - 9.13. Lobe and segment of each biopsy specimen.
 - 9.14. Any medical intervention performed in the bronchoscopy suite or in the recovery suite for stabilization of the patient’s medical condition during or following the procedure, including hemostasis, management of cardiac events, and management of respiratory events.

Outcome Measures

Primary Efficacy Outcome

The primary efficacy outcome of the PROPHET Study is the prevalence of major hemorrhage as defined by two independent reviewers who will review the procedure video while blinded to the individual patient information, study drug assignment, and any procedure related data not recorded on video. Hemorrhage will be graded according to a grading system suggested by

Pilarczyk *et al.* (43) and modified in accordance with the PROPHET Study scientific question as follows:

Grade	Description
No hemorrhage	No hemorrhage
Minor	Endobronchial hemorrhage resulting in segmental or more distal bronchus blood spillage
Intermediate	Endobronchial hemorrhage resulting in lobar bronchus blood spillage
Major	Endobronchial hemorrhage resulting in mainstem bronchus, more proximal blood spillage, or spillage into the uninvolved lung

Secondary Efficacy Outcomes

1. Occurrence of no, minor, or intermediate bleeding as defined by the independent reviewer.
2. Likert scale grading of bleeding by independent observer on a scale of 1 to 5:

1	2	3	4	5
Much less than usual for TBLB	Less than usual for TBLB	Usual for TBLB	More than usual for TBLB	Much more than usual for TBLB

3. Intra-procedural grading by the performing bronchoscopist according to procedure-related outcome as described by Ernst *et al.* and Herth *et al.* (31,44):

Grade	Description
No hemorrhage	No hemorrhage
Mild	Any bleeding originating from the biopsy target airway requiring wedging of the bronchoscope or “in and out” motion in order to achieve hemostasis

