Data are expressed as means with standard deviations, medians with interquartile range, percentages, and proportions as appropriate. Continuous outcome variables were visually examined for normality and outliers using histograms and scatter plots. The normal distribution was assessed with the Shapiro-Wilk test. Continuous variables were compared with the Student's t-test for normally distributed data with similar variance and the Mann-Whitney tests for non-normally distributed data. Proportions were compared using Chi-squared or Fisher's exact tests as appropriate. Statistical significance was set at $P<0.05$. All statistical analyses were performed based on original assigned groups and using Stata software, version 14 (Stata Corp LLC).

Potential Benefits

We hypothesize that prophylactic instillation of topical epinephrine prior to TBLB will reduce procedure-related hemorrhage, leading to lower rate of prematurely aborted procedure due to bleeding complications and higher yield of intended biopsies. The participants may, therefore, have direct benefit from participation if prophylactic topical epinephrine reduces the rate of procedure related hemorrhage in TBLB therefore avoiding early termination of procedure and more intended biopsies taken providing a higher diagnostic yield.

No financial reimbursements or incentive for participating in the PROPHET study will be provided.

Potential Risks and Discomforts

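### The plan does not tie its efficacy conclusion to the primary outcome: Aims 2 and 3 rest on non-primary items, and one P<0.05 rule covers all 13 secondary outcomes

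*Combined protocol and SAP*

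**What the plan says.** Outcome Measures names one primary: "The primary efficacy outcome of the PROPHET Study is the prevalence of major hemorrhage as defined by two independent reviewers". It then lists 13 numbered secondary efficacy outcomes. They run from the lower video grades and a Likert score, through the bronchoscopist's grade, biopsy counts, early termination, duration and hemostatic measures, to whether a pathologic diagnosis was reached.

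The Hypothesis section predicts less frequent and less extensive bleeding, and also "fewer procedures being aborted earlier than intended due to bleeding complications as well as shorter overall procedure time".

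Under Specific Aims, Aim 2 reads "Evaluate the hypothesis that prophylactic administration of topical epinephrine results in reductions in TBLB-related hemorrhage in lung transplant recipients, including". Its four items are the active measures taken against bleeding, completion of the planned biopsies, single- versus double-lung recipients, and clinical risk factors. Major hemorrhage on video is not among them; grading of the video appears only under Aim 1, which concerns feasibility. Aim 3 reads "Evaluate the hypothesis that prophylactic administration of topical epinephrine affects the overall efficiency of bronchoscopy with TBLB performance, including" and lists duration, completion and sample adequacy. Only Aim 4, on safety, is worded as exploring a hypothesis.

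The statistical methods paragraph under Data Analysis gives the tests ("Proportions were compared using Chi-squared or Fisher's exact tests as appropriate"; "Continuous variables were compared with the Student's t-test for normally distributed data with similar variance and the Mann-Whitney tests for non-normally distributed data") and one threshold: "Statistical significance was set at $P<0.05". It has no multiplicity adjustment, no order among the secondary outcomes, no exploratory label, and no sentence linking the efficacy conclusion to the primary.

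**The concern.** Naming one primary normally settles the multiplicity question, because readers take the secondaries as supportive. Here the aim that carries the bleeding hypothesis is itemised entirely with non-primary measures, and the same threshold applies to all of them. A report that followed the plan to the letter could state that epinephrine reduces biopsy-related hemorrhage, or makes the procedure more efficient, on one nominally significant secondary result while the primary shows nothing.

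That situation is not remote. With about 50 procedures per arm and an uncommon primary event, the primary will often be null even if the drug works. Any positive statement would then tend to come from the outcomes without error control.

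**Working it through.** **Inputs from the documents.** There are 13 secondary efficacy outcomes (Secondary Efficacy Outcomes). The threshold is 0.05, with sidedness not stated; two-sided is assumed. The final analysis covers 100 procedures (Overview), allocated by coin toss, so about 50 per arm. The tests are those named under Data Analysis. The documents state no familywise error rate, so there is no figure of theirs to reproduce.

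**Inputs that are assumptions.** These are the event rates, the correlation between outcomes within a procedure, and independence between procedures.

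**Step 1: independent tests.** The chance of at least one P<0.05 under no effect is 1 − (1 − α)^k.
- Either direction, k = 13: 1 − 0.95^13 = 48.7%.
- Favouring epinephrine only, each test having 0.025 in that direction: 1 − 0.975^13 = 28.0%.

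**Step 2: correlated tests.** Thirteen two-sided z-tests with a common correlation, 400,000 runs per setting:

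| Correlation | Either direction | Favouring epinephrine |
|---|---|---|
| 0 | 48.6% | 28.0% |
| 0.2 | 45.1% | 23.7% |
| 0.5 | 33.4% | 16.8% |
| 0.8 | 19.2% | 9.6% |

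**Step 3: outcomes shaped like the listed ones.** Trials of 50 versus 50 were simulated. Items 2 and 3 (graded) and items 4, 5, 7, 8 and 9 (continuous) were compared by Mann-Whitney. Items 1, 6, 10, 11, 12 and 13 (binary) were compared by chi-squared, or by Fisher's exact test when an expected count was below 5. The assumed rates for those six were 50/5/1/1/5/60% (rare) or 50/20/5/5/10/60% (commoner). Fisher's test is conservative for rare events, so items such as hemostatic procedures add little, and the totals fall below those of step 1.
- Favouring epinephrine: about 15-19% at correlation 0.5, and about 10-27% over correlations 0 to 0.8.
- Either direction: about 20-46% over the same correlations.

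**Step 4: how likely is a null primary?** Power is the sum, over all pairs of event counts, of the two binomial probabilities wherever the test gives P<0.05. With 50 per arm, the same test rule, and epinephrine assumed to halve the rate:
- control rate 4%: below 1%
- 12%: 14%
- 13%: 16%
- 20%: 30%

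The table under Sample Size and Power Calculations gives published rates between 0.5% and 13%, apart from one study at 44.5% with 15 listed procedures, which would give 66%. Those rates mostly use blood-volume definitions, not the video scale, so they only indicate the likely region.

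**Step 5: the count of 13.** It counts listed items, not planned tests. Item 1, "Occurrence of no, minor, or intermediate bleeding as defined by the independent reviewer", is the complement of the primary if taken as one category, and then adds no new test. Dropping it gives 1 − 0.975^12 = 26.2% favouring epinephrine and 1 − 0.95^12 = 46.0% in either direction under independence. Splitting it by grade would push the count the other way. The bronchoscopist's grade overlaps items 6, 8, 9 and 10, which raises the correlation. None of this brings the error near the nominal level.

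**The case against.** The other side has several fair points.

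- **A ranking exists.** One outcome is headed primary and the rest secondary. A reader might infer that the plan has no hierarchy at all; that is wrong. The gap is among the secondaries and in the aims.
- **The trial is a pilot.** The Overview says so, and the sample size rests mainly on feasibility. Unadjusted secondaries are common in such trials. This limits the consequence. It does not supply the missing label, because Aims 2 and 3 are worded as evaluating hypotheses, and the protocol also asks whether the local dose and volume are effective in prevention.
- **Aim 2's list is introduced as inclusive.** Omitting the primary does not formally demote it. True, but a reader still cannot tell from the aim which result decides it.
- **Direction matters.** A significant secondary against epinephrine cannot produce a false claim of benefit. The favourable-only figures are therefore the ones that measure the harm, and they are about half the two-direction ones.
- **The Hypothesis section joins its parts.** A reader might infer that success on any one part would confirm it, and compute an error rate on that basis. The text links the parts cumulatively, and if all were required the error would be below 5%. No inflation figure for that hypothesis is supported.
- **The threshold is stated generally.** The plan does not list 13 tests, and nowhere says that a secondary alone would establish efficacy. The point concerns what the plan leaves open, not what the sponsor intends.

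**Conclusion.** The point holds in a limited form. The plan ranks its outcomes but does not make the efficacy conclusion depend on the primary, and Aims 2 and 3 can be read as met on a single nominal secondary result. For an inert drug, the chance of at least one such result favouring epinephrine is about 15-19% at correlation 0.5 and about 10-27% over correlations 0 to 0.8, against 2.5% for a single two-sided test in that direction. In either direction it is about 20-46%, or 49% for 13 independent tests, against 5%. All of these rest on assumed event rates and correlations that the documents do not give, and on a fair reading that each listed outcome is tested. A single precise figure would claim more than the documents allow. The gap affects what may be concluded and should be closed; it does not invalidate a pilot trial.

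**What to change.** Add to the statistical methods paragraph under Data Analysis: *The efficacy conclusion rests on the between-arm comparison of major hemorrhage, at a two-sided level of 0.05. The secondary efficacy outcomes and Aim 3 are exploratory and are reported as between-arm differences with 95% confidence intervals. A P value below 0.05 on any of them will not be reported as showing that epinephrine reduces bleeding or improves efficiency.*

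List the primary outcome under Aim 2, so that the aim and the outcome section point to the same comparison.

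The change needs no more patients, data or procedures. A formal adjustment is not needed on this route; for reference, Bonferroni over 13 outcomes would require 0.05/13 = 0.0038 per test. The small cost is that a lone significant secondary could serve only as a lead for a later trial.
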